8.4 DESIGN: Briefly describe the study design (e.g., observational, interventional, randomized, placebocontrolled, blinded, cross-over, cross-sectional, longitudinal, pharmacokinetic, etc.):

Design & Procedures

1. Subject recruitment: Participants will be recruited in [name] laboratory at UCSF. We plan to enroll a total of 240 subjects healthy volunteers (age range: 21-65 years) in order to complete 100 for the entire effort (R21 and R33 Phases combined). This corresponds to enrolling 68 subjects in the R21 (34/year) and 172 (58/year) during the R33 phase. This takes into account the expected rate of failure to: have a pupillary response to the fear conditioning paradigm (25%) and CO₂ challenge (50% - relevant for last 10 R21 and all R33 subjects); and to meet other screening criteria (see inclusion and exclusion criteria sections). These subjects will be recruited from the local community using posted flyers.

2. R21/R33 Components: R21 Phase:

First 30 Subjects, following the screening visit, these subjects will undergo 2-3 sessions separated by 1 week in which a promising electrode configuration (three promising configurations will each be tested in a cohort of 10 subjects) will be used with tDCS stimulation at increasing electrical dosage during which pupillometry will be carried out to determine the Anxiety Task (a test of responses to electrical pulses delivered to the fingers) or Auditory Oddball Test (AOT; a test of responses to rare vs common sounds) response. During pupillometry while undergoing tDCS, ECG, EEG, respiratory rate, or galvanic skin conductance measures may be obtained. A maximum of 5 total tDCS dosages and sham will be tested.

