R33 Phase: 60 subjects will participate in a double-blind, randomized, controlled, parallel-group trial. They will be randomized to either active or control treatment and at the first post-screening visit they will undergo electrical dose titration as described above for the treatment they are randomized to. For all titrations, during the 5 minutes between tDCS treatments an unblinded member of the study team not having contact with the subjects will compute their Anxiety Task or Auditory Oddball Test response (these tests will be used to determine optimal dosing in terms of the tDCS level that blocks the pupil response in these tests) and convey to the tDCS treatment physician whether to continue or stop titration. Subjects randomized to the control treatment will undergo a sham titration where the stop level will be randomly selected from the distribution of titration outcomes occurring in the R21 phase. Subjects will then return in 1 week and undergo optimal dose tDCS or control treatment for a single treatment session as described in the prior paragraph. Primary outcome will be the VAS-A "fearful" rating obtained at the end of tDCS/CO₂ inhalation. Anxiety Task or AOT pupil responses will be obtained every 10 minutes after the end of the tDCS/CO₂ inhalation period to map the duration of persistent effects on LC (heart rate and skin conductivity will also be obtained as exploratory measures). At the end of this session participation will end except that subjects will be called the next day to assess for adverse effects and care given if necessary. Data from the R21 phase will be used to provide justification for the larger R33 study, and prior to initiation of the R33 phase, the study will be submitted to the IRB for review/approval.

8.5 BACKGROUND AND SIGNIFICANCE: Briefly provide the background and significance of this study (e.g.

why is this study needed) (space limit: one half page):

If this is a first in humans study, please summarize the safety data from the animal studies. For pediatric drug or device studies, please identify if this is the first study in pediatric populations.

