It is important to note that the 4 mA maximum dosage is within recommended safety limits. We evaluated tDCS with: 1) the electrodes placed over the ears (external auditory meatus) and; 2) one electrode at the inion (notch on the back of the head at the top of the neck) and the other just under the chin. Pupillometry was carried out during the auditory oddball tasks (AOT) where two tones are played one more frequently than the other and the rare tones are well-established to lead to a neural response approximately 300 msec after the rare tones are played. We found that treatment was well-tolerated in general. We were able to find at least one electrode configuration and polarity (orientation of anode and cathode) associated with a tolerable stimulus intensity for all subjects that had a statistically significant effect on the pupillary AOT response. In 4/5 subjects there was an electrode configuration where the LC pupil dilation response to the rare stimuli was significantly suppressed by tDCS compared with both immediate pre and immediate post-stimulation testing (see Figure 3 for example). In 1 subject the response to the rare tones was enhanced by stimulation. In two of the subjects the direction of effect (suppression or enhancement) differed for the electrode configurations and polarities tested. These findings suggest that we can modulate LC function with tDCS with a substantial effect size, though the findings further indicate that electric field modeling will be needed to determine optimal treatment electrode placement given that effects appear to vary from person-to-person and that it is not possible to predict effects in a simple way, such that without modeling and iteration, we may be as likely to augment as inhibit LC activity, at least in some individuals. The findings also indicate that the effect size of inhibition is large enough to be statistically significant at the $p<0.05$ level in a single trial in an individual. These findings serve as a key basis for the proposed effort, support the need for work to determine optimal electrode placement before trials of tDCS for acute fear could be carried out, and support the use of the AOT as a target engagement measure.

8.7 * TREATMENT PROTOCOL: Is this a treatment study, i.e. does this study intend to provide treatment to individuals with a medical or psychological condition: (REQUIRED)

Yes No

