2. **Transcranial Direct Current Stimulation (tDCS):** tDCS involves non-invasive transcranial electrical stimulation using direct current with a sustained intensity of a few milliamperes and duration of up to tens of minutes. Administered in this way tDCS is a safe procedure (See Bickson et al., 2016 attached). Evidence from relevant animal models indicates that brain injury by such Direct Current Stimulation occurs at predicted brain current densities (6.3–13 A/m) that are over an order of magnitude above those produced by tDCS such as we will administer it (Bickson et al., 2016). To date, the use of conventional tDCS protocols in human trials (40 min, 4 milliamperes, 7.2 Coulombs) has not produced any reports of a Serious Adverse Effect or irreversible injury across over 33, 200 sessions and 1000 subjects with repeated sessions and including a wide variety of subjects, including persons from potentially vulnerable populations (Bickson et al., 2016). tDCS will be administered with a multichannel direct current stimulation device (NeuroConn DC stimulator MC-4, neuroCare). This device can be programmed so that the operator doesn't know the combination of electrodes being used for stimulation, and, thereby allow double-blinding. The active tDCS electrode configuration to be used will be determined with the 3 round iterative procedure described above; based on electric field modeling and personalized electrical dose titration to find the lowest dose that is well-tolerated and engages the

target in terms of inhibiting the Anxiety Task or AOT pupillary response and pain-induced conditioned fear response. Electrical dosage will be personalized for each subject by titrating dosage (gradually increasing) until the dosage is found that is both well-tolerated (no more than mild discomfort on a 5-point Likert scale) and suppresses the pain-induced conditioned fear response. If the 5-point Likert tolerability rating is greater than "mild discomfort" or if maximum amperage is reached without effect on the conditioned fear response then subject participation will terminate.

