3. **Anxiety Task:** Using the eye-tracking system to track pupil changes, the subject may undergo the anxiety task which involves two different epochs: high tone and low tone. Before the anxiety task begins, the level of "annoying buzz" will be determined for the subject by the research team, based on the verbal responses from the subject. First, a low level "buzz" (set at 5V) will be presented through stimulation generated to the index and middle fingers of the subject, using the BIOPAC STM-200 Stimulator (duration of less than 0.5 seconds) by the researchers. The subject will be asked to report on a scale of 0 (not at all annoying) to 10 (extremely annoying), how the stimulus feels. The presentation of the "buzz" will increase in increments of 5-10V (with a maximum of 100V) until the subject reports a level 7 for highly annoying. The purpose of this "annoying buzz" is to be highly annoying, but not to provoke pain. Once this level is set, the anxiety task is initiated during which the subject will be seated in a dark room and instructed to focus on crosshairs displayed on a computer monitor. The anxiety task consists of two block types: (1) high tone and (2) low tone. Two tones of different frequencies (high and low) are played for 5 seconds at a time throughout a trial. Each trial lasts 12 minutes and consists of each tone (high and low) played 20 times (totaling to 40 tones at 5 seconds each). Stimulation will be delivered 50% of the time in association with either the high or low tone in a given trial (subject receives stimulation 10 times per trial). At each study visit (up to 3 visits, scheduled one week apart) for subjects 1-30, the subject will complete 4-6 trials during which tDCS will be administered at gradually increasing electrical doses during 50% of the trials. The other 50% of the trials will be administered without tDCS or with sham tDCS to establish the subject's baseline pupil response to the anxiety task. Subjects will be given a 5 minute break between each trial.

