decrease the "buzz" stimuli to the patient's level of comfort, as they self-report "annoying" but not "painful" level. The patient may stop at any time or have the stimulus reduced at any time. The number of stimulations delivered will be limited to 10 per 12 minute trial (stimulation associated with either the high or low tone). Parts of the task may become boring or repetitive. Efforts will be made to limit the number of trials administered per visit to minimize subject boredom and discomfort, while ensuring that adequate amounts of data are being collected.

Inhalation of 7.5% CO₂. The primary adverse effect of 7.5% CO₂ inhalation is the induction of Acute Fear which is also the reason that it is being carried out in this study. The fear is generally well-tolerated and resolves within roughly 10 minutes of the end of inhalation. A small percentage of subjects report increased sweating, tremor, tension, and tight muscles during or shortly after inhalation which is generally well tolerated. A gradual rise in blood pressure and pulse with a final systolic blood pressure rise of approximately 18 points, diastolic blood pressure rise of approximately 3 points, and heart rate elevation of approximately 8 points occurs with CO₂ gas as compared to when subjects received "air" inhalation. In rare circumstances severe anxiety could be elicited. There is no evidence that repeated inhalations increases the risks of severe anxiety in response to inhalation testing or in the year following the inhalations. Several studies have evaluated the effects of repeated inhalations with 7.5% CO₂ and higher percentages of CO₂ and not found evidence that there is an increase in fear elicited or an increase in adverse effects with repeated exposures (Poma et al., 2005; Verburg et al., 1998). In addition, a group of healthy non-anxious subjects undergoing repeated exposure to 20% CO₂ inhalation (N=155) were followed for up to a year and compared to a group of healthy non-anxious control subjects who breathed room air (N=56) and there was no evidence that the exposures to 20% CO₂ increased the risk for anxiety /panic during the year of follow-up (Prenoveau et al., 2006).

ECG. Skin irritation from the ECG electrode pads or pain when removing the pads is a possible risk.

12.3

MINIMIZING RISKS: Describe the steps you have taken to minimize the risks/discomforts to subjects. Examples include:

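### The suppression rule makes no comparison with neighbouring off or sham trials, so with ascending tDCS levels any waning of the task response would be counted as tDCS suppression

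*Combined protocol and SAP*

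**What the plan says.** Levels ascend wherever the order is described. Section 8.4 says that each configuration "will be used with tDCS stimulation at increasing electrical dosage during which pupillometry will be carried out". Section 8.9 (item 2) personalises the level by "titrating dosage (gradually increasing) until the dosage is found", and item 3 says "tDCS will be administered at gradually increasing electrical doses during 50% of the trials". No randomised or counterbalanced order is given.

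At each visit for subjects 1-30 "the subject will complete 4-6 trials" of the Anxiety Task. A trial lasts 12 minutes, has 20 high and 20 low tones, and is followed by a 5-minute break. Item 3 continues: "The other 50% of the trials will be administered without tDCS or with sham tDCS to establish the subject's baseline pupil response". Where those trials fall in the series is not stated. Section 12.2 adds, about the buzz, "The patient may stop at any time or have the stimulus reduced at any time".

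The last 10 R21 subjects may have up to five levels tested in one session (8.4). The R33 paragraph of 8.4 places the reading of the response as follows: "For all titrations, during the 5 minutes between tDCS treatments". It mentions no off trial after a level.

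The scoring rule is in 8.25 (R21, Hypothesis 2a). The two task conditions are compared during treatment, and only a significant difference counts as failure to suppress. Success is 8 of 10 subjects. The interim-analysis text in 13.2 instead asks for statistically significant inhibition, without naming a comparator. In the pilot (8.6), 4 of 5 subjects showed suppression "compared with both immediate pre and immediate post-stimulation testing".

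**The concern.** Within a visit a higher level is always a later trial. A response that weakens with repetition, or because the buzz has been turned down, therefore looks the same as suppression by a higher level. Off or sham trials on both sides of each level could separate the two explanations. The plan includes such trials, but it neither fixes their place nor uses them in the rule.

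This reading decides the 8/10 count, the configuration carried forward and each active subject's level. The R33 control stop levels are drawn from R21 titration outcomes (8.4), so an error would also reach the control titration. A level recorded as effective only because the response waned would not engage the target, and that pulls the R33 comparison towards no effect.

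**Working it through.** **The plan's own figure.** There is none to reproduce: no power, error rate or waning rate is given for this rule.

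**Inputs from the documents.** 20 tones per condition per trial; 4-6 trials per visit, half with tDCS; up to five levels; success at 8/10.

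**Assumptions.** A two-sample t test of 20 against 20 tones (38 df, two-sided 5%) stands in for the planned repeated-measures analysis. Trials are independent. The tDCS effect is zero. First-trial power is 90%, that is d = 1.052 and noncentrality 1.052 × √10 = 3.33. The response is multiplied by (1−h) at each trial.

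**Step 1: the 8.25 rule, per subject.** The power at trial k is π_k = P(|T₃₈| > 2.024) with noncentrality 3.33(1−h)^(k−1). With order off-on-off-on-off-on, the chance that at least one of three levels is called suppressing is 1 − π₂π₄π₆.

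**Step 2: the cohort.** P(X ≥ 8) with X ~ Binomial(10, p).

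| Waning h | π₂, π₄, π₆ | p per subject | P(≥8/10) |
|---|---|---|---|
| 0 | 0.900, 0.900, 0.900 | 27% | 0.1% |
| 5% | 0.869, 0.794, 0.708 | 51% | 6% |
| 10% | 0.831, 0.657, 0.482 | 74% | 49% |
| 20% | 0.737, 0.382, 0.186 | 95% | 99% |

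Other layouts at h = 0, 5, 10, 20%:
- Three off trials, then three on: p = 27, 58, 82, 98%; P(≥8/10) = 0.1, 13, 74, >99%.
- One off trial, then five levels in one session: p = 41, 69, 89, 99%; P(≥8/10) = 1.4, 37, 91, about 100%.

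Sensitivity to first-trial power, alternating layout: at 10% waning, p is 85% if that power is 80% and 39% if it is 99%. With 99% power and 5% waning, p is 14% and P(≥8/10) is below 0.1%.

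**Step 3: a direct contrast against earlier off trials only.** Normal approximation with noncentrality 1.96 + 1.28 = 3.24.
- Mean of off trials 1-3 against on-trial 6, 10% waning: shift = 3.24 × (0.903 − 0.590)/√(4/3) = 0.88, so a two-sided test is significant in 14% of subjects. At 20% waning: 3.24 × (0.813 − 0.328)/√(4/3) = 1.36, giving 28%.
- Trial 1 alone against trial 6: 16% and 34%.
- These single-contrast rates give P(≥8/10) below 0.4%. If any of on-trials 4-6 may count against off trials 1-3, in the suppression direction, the rates are 26% and 45%, and P(≥8/10) is below 3%. The most extreme case tried (first off trial as comparator, 99% first-trial power, 20% waning) gives 62% per subject and P(≥8/10) of 20%.

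**Step 4: a bracketed contrast.** The mean of the two adjacent off trials minus the on-trial between them leaves a residual of h²/2 of the response at the first trial of the bracket, that is 0.005 or 0.02. For a bracket starting at trial 1 the larger value gives a shift of 3.24 × 0.02/√1.5 = 0.05, and the two-sided rate stays at 5.0%. That is for one test. In the suppression direction over five levels it is about 1 − 0.975⁵ = 12% per subject if the tests are independent, so the error rate has to be set for the number of levels. Requiring the on-trial to be significantly below both neighbours, as in the pilot comparison, gives about 1.3-1.4% per subject over three levels at every waning rate tried.

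**The case against.** Several counter-arguments stand.

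- **A within-visit control exists.** Half the trials for subjects 1-30 are off or sham, and nothing forbids placing some after a tDCS trial. Levels may also be spread over weekly visits. This limits the concern but does not remove it: order still ascends within a visit, and the rule does not use those trials.
- **Waning is assumed.** The nearest text, in 12.2, says only that the task may become boring or repetitive. A reader might infer that habituation is already being scored as suppression; the documents support only that it would be if it occurred.
- **Part of the inflation is not waning.** Reading non-significance as suppression over three looks already gives 27%. Under the significant-inhibition wording of 13.2 the cohort-level risk is mostly small (Step 3).
- **A false Go to R33 is tempting to infer, but does not follow.** Section 8.25 also requires active tDCS to suppress the pupil response to CO₂ in a cross-over with randomised order and sessions a week apart. Waning within a task series cannot by itself produce that result. The DSMB and NIH also assess the Go criteria (13.2).
- **It is tempting to say that the pilot's safeguard was dropped.** Section 8.6 reports how the pilot result was judged; it does not set a scoring rule. The later sections are silent rather than contrary.
- **The buzz argument applies to the Anxiety Task only.** The oddball alternative has no buzz.

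**Conclusion.** The concern holds in conditional form. Levels ascend, off and sham positions are open, and the 8.25 rule would count a waned response as suppression. With first-trial power of 90% and no tDCS effect, 5-20% waning per trial raises the per-subject false-suppression rate from 27% to 51-95% in the alternating layout, and the chance of 8/10 from 0.1% to 6-99%. Only the excess over 27% is due to waning. The size depends on assumed starting power, waning rate, independence and sidedness, and it is small when responses are very strong and waning is slight. The consequence is a configuration or individual level carried forward without evidence that it engages the target, with likely dilution in R33. The CO₂ cross-over remains a separate check before a Go.

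**What to change.** In 8.9 and 8.25:

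1. Place an off trial, preferably sham, before and after each tested level. In the single-session titrations this includes one after the level chosen.
2. Define suppression as a direct test that the condition contrast in the tDCS trial is smaller than in the adjacent off or sham trials, with the error rate set for the number of levels tested.
3. For the Anxiety Task, compare only trials run at the same buzz voltage.
4. Reconcile 8.25 and 13.2 on this one definition.

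Costs:
- Off-on-off-on-off takes 5 × 12 + 4 × 5 = 80 minutes. That leaves 10 minutes of a 1.5-hour visit (11.13) for set-up; repeating an off trial after a buzz change adds 17 minutes.
- It makes 2/5 = 40% of trials active, so the 50% split must be edited.
- It tests two levels per visit, so two sessions hold four levels and three hold up to six.
- Bracketing five Anxiety Task levels in one session needs 11 trials, 11 × 12 + 10 × 5 = 182 minutes, against the 2-2.5 hours planned. Fewer levels fit, or the visit is longer.
- A lasting after-effect of tDCS would prevent recovery and make the count conservative.

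No level or clinical rule needs to change.

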Last 10 Subjects. These subjects will take part in a double-blind, controlled, randomized, cross-over study over 3 sessions following their screening visit. At session 1 subjects will undergo electrical dose titration with the tDCS electrode configuration resulting from the 3 rounds of optimization using the same procedure as in the first 30 subjects to determine the lowest well-tolerated dose that suppresses the pupil dilation response to the Anxiety Task or Auditory Oddball Test, except that a maximum of 5 tDCS dosages will be tested at this session. At the second and third sessions (1 week apart) subjects will receive doseoptimized tDCS and the control treatment with order randomized along with 7.5% CO₂ (to evoke an LC response) for 20 minutes. The 7.5% CO₂ will be delivered pre-mixed as provided by Airgas. 7.5% CO₂ is commonly and safely used in the field of study. A mixture of CO₂ 7.5%/O₂ 21%/N 71.5% will be purchased premixed from Airgas and shipped to UCSF. At these sessions, the VAS-A and STA-I will be administered 5 minutes prior to and just after the 20 minute session and VAS-A will also be obtained at 5, 10, 15, and 20 minute points of the CO₂ inhalation. tDCS will be administered during the last 5 minutes of the 20 minute CO₂ inhalation period. Subjects will be monitored for an hour post-session for safety and will undergo study physician assessment to determine suitability to leave. Following the 2nd treatment session participation will end except that subjects will be called the next day to assess for adverse effects and appropriate care will be given if any are found.

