3. **Visual Analogue Scale for Anxiety (VAS-A).** The VAS-A is the primary measure of clinical symptoms of Acute Fear in both the R21 and R33. It has been used extensively as an indicator of acute fear symptoms. It is included because it provides a reliable indicator of rapid changes of affective state and is sensitive to the fear-inducing effects of 7.5% CO₂ in healthy volunteers. VASA consists of 11 items for 11 different symptoms (anxious, alert, fearful, relaxed, happy, feel like leaving, paralyzed, tense, nervous, irritable and worried) where for each item a mark is made on a 100 mm line scaled from 0 (not at all) to 100 (the most ever) to indicate symptom severity. The "Fearful" item will be used as the single primary endpoint due to its being consistently significantly increased in prior studies of CO₂ administration to healthy controls and evidence that anxiolytics can prevent 7.5% CO₂ mediated increases in this measure. The other 10 VAS-A items will be secondary outcomes. For each CO₂ administration ratings will be carried out at baseline (5 min prior to inhalation), and at 5, 10, 15, and 20 minutes into the inhalation and 15 minutes after inhalation ends. The peak effect will be obtained immediately after the end of the inhalation when the subjects will be asked to retrospectively rate the greatest intensity of effects experienced. A 26% increase in peak effect over baseline on the "fearful" item will be utilized as criteria for responding to CO₂ challenge as recommended based on prior work which suggests that approximately 50% of subjects will meet this criterion. The VAS-A "fearful" rating at 20 minutes from the start of CO₂ administration will serve as the primary outcome measure with the rating of peak effect being a key secondary outcome. The VAS-A may also be used during the anxiety task before, during, or after to measure changes in levels of subject anxiety from baseline to post-task administration.
4. **State Trait Anxiety Inventory (STAI).** The 20 item STAI will be included as a secondary clinical symptoms measure of state anxiety occurring with CO₂ administration. This was included because it has well-established psychometric properties and reflects changes in anxiety level with CO₂ administration in healthy controls and anxiolytic medication attenuated the CO₂ response with this measure. It consists of 20 items listing feelings and subjects rate their

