2) Hypothesis 1b: In 10 controls in a cross-over study, 7.5% CO₂ inhalation significantly increases the VAS-A "fearful" rating compared to baseline rating. This will be tested with a RMANOVA where condition (7.5% CO₂ vs air) is the independent variable and VAS-A "fearful" rating is the repeated dependent measure.

3) Hypothesis 2a, 1b, 1a: In a cross-over study, active dose-personalized tDCS significantly suppresses the LC pupil response to 7.5% CO₂. This will be tested by carrying out a RMANOVA where treatment (active tDCS vs control) is the independent variable and mean resting pupil diameter is the repeated dependent measure. This will also establish that 7.5% CO₂ elicits an LC response as measured by mean pupil diameter (Hypothesis 1b) and whether subjects can guess whether they received active tDCS or the control to assess the viability of the control treatment (Hypothesis 1a).

4) Hypothesis 2b: Active tDCS will be safe in terms of there being no adverse effects of more than mild severity and rated to be possibly, probably, or definitely related to treatment.

R33 Testing R33 hypotheses assesses if the criteria for proceeding to further development are met.

1) Hypothesis 3a: Dose-personalized tDCS decreases VAS-A "fearful" rating compared to sham in a parallel-group, randomized, double-blind study. This will be determined by computing the effect size in terms of Cohen's D for the tDCS vs control treatment effect on the VAS-A "fearful" rating at the expected peak CO₂ effect (20 minutes after start of CO₂).

2) Hypothesis 3b: tDCS is safe as indicated by the absence of adverse effects of more than mild severity rated to be possibly, probably, or definitely related to treatment.

Secondary/Exploratory Analyses. Examples of Exploratory/Secondary analyses of interest include: 1) Testing if there are significant differences between active tDCS and the control therapy on the pupillary response to CO₂ in the R33 study; 2) Evaluating tDCS vs control treatment effect sizes for

other VAS-A items and the STAI in the R33 study; 3) mapping the time-course of effects on LC post-tDCS

8.26 REFERENCES: List only the 5-10 most relevant references (a separate bibliography can be attached for reference purposes if this study involves novel approaches, agents, or an emerging technology that the IRB may not be familiar with):

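### The key secondary peak-fear rating most naturally covers all 20 minutes of CO₂ but tDCS runs only in the last 5, so it will tend to understate an effect seen at minute 20

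*Combined protocol and SAP*

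**What the plan says.** Section 8.4 (R21 Phase, Last 10 Subjects) fixes the timing of stimulation: "tDCS will be administered during the last 5 minutes of the 20 minute CO₂ inhalation period". It also sets the timed ratings: "VAS-A will also be obtained at 5, 10, 15, and 20 minute points of the CO₂ inhalation". The R33 Phase paragraph carries this session over, since R33 subjects "undergo optimal dose tDCS or control treatment for a single treatment session as described in the prior paragraph".

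Section 8.11 (VAS-A) defines two outcomes on the 'fearful' item. For the primary, the "rating at 20 minutes from the start of CO₂ administration will serve as the primary outcome measure". The other is the peak effect, a single recalled rating taken when the inhalation ends, at which "subjects will be asked to retrospectively rate the greatest intensity of effects experienced". Its rank is stated too: "with the rating of peak effect being a key secondary outcome". The same peak, compared with baseline, defines response to CO₂ (a 26% increase).

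Section 8.25 tests Hypothesis 3a by Cohen's d on the minute-20 rating and names minute 20 as the time when the CO₂ effect should be greatest. Its secondary analyses, listed as examples, do not mention the peak rating. Section 10.3 gives no power or effect size for any VAS-A outcome.

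**The concern.** The rating and the treatment cover different periods. A recalled maximum over the inhalation takes in 15 minutes without current (15/20 = 75%) and 5 minutes with it. Fear already reached when current starts is part of the maximum in both arms, and tDCS cannot undo it.

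Treatment that starts at minute 15 could act by lowering fear that is already present. The minute-20 rating can register that, but an accurately recalled whole-inhalation peak cannot. If tDCS works, a clear minute-20 effect beside a smaller or null peak effect is therefore a likely pattern. The plan does not say how to read the two together, so the weaker key secondary could be taken as a failure to support the primary when the recall window alone explains the gap.

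**Working it through.** The plan states no figure for the peak rating, so there is none to reproduce.

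**Inputs from the documents.** Current in minutes 15–20 and timed ratings at 5, 10, 15 and 20 minutes (8.4); peak recalled once at the end with no start point (8.11); greatest effect expected at minute 20 (8.25).

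**Inputs that must be assumed.** The time course of fear, its SD, the correlation between ratings and the tDCS effect. None is in the documents.

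**Step 1: one subject, accurate recall.** Let A be the highest fear in minutes 0–15 and B the highest in minutes 15–20. Then peak = max(A, B). tDCS can change only B, so the peak under tDCS is at least A. Take untreated fear of 50 at minute 20 and a 20-point tDCS effect there:

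| Fear at min 15 | Untreated peak | Peak with tDCS | Peak difference | Min-20 difference |
|---|---|---|---|---|
| 50 | 50 | 50 | 0 | 20 |
| 45 | 50 | 45 | 5 | 20 |
| 40 | 50 | 40 | 10 | 20 |
| 30 | 50 | 30 | 20 | 20 |

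If a share f of the subject's untreated peak rise is reached before current, the peak can fall by at most (1 − f) of that rise: 50% at f = 0.5, 25% at f = 0.75 (a straight-line rise, 15/20), 10% at f = 0.9, and 0 at f = 1.

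**Step 2: this limit does not carry over to arm means.** When subjects differ, some are still rising after minute 15 even if the mean is flat, and the mean of max(0, B − A) is at least max(0, mean B − mean A). With f applied to the mean curve, the simulation in step 3 (0.80 SD effect) gives a mean peak difference of about 0.15 to 0.24 SD at f = 1, where the single-subject limit would give 0. At f = 0.9 with a rise of 1.0 SD it gives 0.19 to 0.21 SD, where the limit would give 0.10.

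**Step 3: simulated size with subjects differing.** Ratings at 5, 10, 15 and 20 minutes, SD 1; adjacent correlation 0.5, 0.7 or 0.9; mean rise in controls of 1.0, 1.5 or 2.5 SD, linear to f × rise at minute 15 and complete at minute 20; tDCS lowers minute 20 only, by 0.80 SD; peak = highest of the four. Repeat runs agree to about 0.01.

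- f = 0.75: d on the peak is 0.26–0.29 (rise 1.0), 0.34–0.36 (rise 1.5), 0.46–0.54 (rise 2.5).
- Lowest case: 0.15 (rise 1.0, f = 1, correlation 0.9).
- Highest case: 0.76 (rise 2.5, f = 0.5, correlation 0.9).
- With a 0.50 SD effect at minute 20, the range is 0.13 to 0.49.

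**Step 4: a different scale.** On a 0–100 scale with clipping, SD 25, correlation 0.7 or 0.9, a control mean of 50 at minute 20 and effects of 10, 15 or 20 points, the peak keeps these shares of the minute-20 difference:

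| Mean fear, min 15 to 20 | Share kept |
|---|---|
| 50 to 50 | 20–33% |
| 40 to 50 | 42–61% |
| 30 to 50 | 58–85% |
| 20 to 50 | 73–95% |

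The peak effect was the smaller one in every scenario.

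**Step 5: the adjusted minute-20 analysis.** If the minute-15 rating precedes current, adjusting for it leaves the 0.80 SD difference intact. The residual SD is √(1 − r²): 0.87, 0.71 and 0.44 for r = 0.5, 0.7 and 0.9.

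**The case against.** **No planned decision uses the peak.** Section 8.25 ties further development to Hypotheses 3a (minute-20 fear) and 3b (safety). This stands. A reader might infer that the R33 go-forward decision or the primary result is biased; the documents do not support that. What is at stake is the reading of a secondary result.

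**The peak is recalled, not observed.** Relief at the end of the session could colour the memory, so a recalled peak might fall below fear felt earlier. This also stands, which is why the argument is conditional on accurate recall. Such a difference would be recall error rather than lower peak fear.

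**The plan expects the greatest effect at minute 20.** This softens the problem. With a steep late rise (20 to 50 in step 4) the loss is 5–27%. It does not remove the problem, because fear before minute 15 still sets the floor and some subjects may peak earlier.

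**The time course can be learned first.** The R21 cross-over takes the same timed ratings, including under the control treatment, and section 8.4 says that the study returns to the IRB before R33. That allows the size to be estimated before R33 starts. It does not define the recall window or the order of events at minute 15.

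**Worst fear is a legitimate separate question.** It is, and section 8.9 lets subjects stop the inhalation at any time. An early stopper may have no on-gas minute-15 or minute-20 rating but can still rate the peak. These are good reasons to keep the peak as an outcome.

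**Conclusion.** The point holds as a matter of structure. With current confined to minutes 15–20 and recall read as covering the whole inhalation, the peak rating can show a blunted further rise but not relief below the pre-current level, and it will tend to understate an effect seen at minute 20. This rests on accurate recall and on that reading of an unstated window.

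The size cannot be taken from the documents. Under the assumed time courses a true d of 0.80 at minute 20 becomes about 0.15 to 0.76 on the peak, from severe loss to almost none.

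Two stronger readings should be resisted. A reader might infer that the arm difference in peak is capped at the control arm's mean rise after minute 15; step 2 shows that this fails once subjects differ. A reader might also infer that the peak cannot show any tDCS effect; it can, wherever fear is still rising at minute 15. The primary outcome, Hypothesis 3a and the R33 development criteria are untouched.

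**What to change.** 1. State in 8.4 and 8.11 that the minute-15 VAS-A rating is completed before current starts. Both now fall at minute 15 with no stated order.
2. Add to 8.25 an analysis of the minute-20 'fearful' rating adjusted for the minute-15 rating (ANCOVA; adjusted mean difference with 95% CI). Say how subjects who stop inhaling early are handled, since they may lack one or both ratings.
3. Keep the peak as a secondary outcome and for the 26% responder criterion. State that it covers the whole inhalation, and note that 15 of its 20 minutes precede current, so a small or null arm difference in it is not by itself evidence against tDCS.

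Shortening recall to the last 5 minutes would not be enough, because that window opens at the minute-15 level.

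Cost: a line on the order of events, an interpretive note and one extra analysis that overlaps with the primary. The ratings are already scheduled; stimulation, primary outcome and sample size do not change.
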